4.2. Secondary endpoints

Safety:

- Occurrence of each solicited local AE, during the 7-day follow-up period (Day 1 - Day 7) following each vaccination.
- Occurrence of each solicited general AE, during the 7-day follow-up period (Day 1 - Day 7) following each vaccination.
- Occurrence of any unsolicited AE, during the 30-day follow-up period (Day 1 - Day 30) following each vaccination.
- Occurrence of any pIMD from first vaccination up to study conclusion.
- Occurrence of any SAE from first vaccination up to study conclusion.

Efficacy: All AECOPD

- Yearly rate of all AECOPD (any cause, any severity) starting 1 month post-Dose 2, in vaccinated and control subjects.
 - Rate of moderate and severe AECOPD cases in vaccinated and control subjects, during 3, 6 and 9 months observation starting 1 month post-Dose 2.
 - Rate of all AECOPD cases in vaccinated and control subjects, during 3, 6, 9 and 12 months observation starting 1 month post-Dose 2.
 - Rate of all AECOPD cases in vaccinated and control subjects, during 3, 6, 9 and 12 months observation starting 1 month post-Dose 2, by severity.
- Time to first moderate or severe AECOPD.
- Time to first AECOPD of any severity.
- Time to first AECOPD, by severity.
- Duration of moderate and severe AECOPDs.
- Duration of AECOPDs of any severity.
- Duration of AECOPDs, by severity.

CONFIDENTIAL

207489 (NTHI MCAT-002)

Statistical Analysis Plan Amendment 2 FDA Final Draft

Efficacy: AECOPD associated to bacteriological pathogens (PCR)

- Rate of NTHi-associated and/ or Mcat-associated moderate and severe AECOPD, over a period starting 1 month post-Dose 2 and lasting for 1 year.
- Rate of NTHi-associated and/ or Mcat-associated any severity AECOPD, over a period starting 1 month post-Dose 2 and lasting for 1 year.
- Rate of NTHi-associated and/ or Mcat-associated AECOPD, over a period starting 1 month post-Dose 2 and lasting for 1 year, by severity.
- Time to first moderate or severe NTHi-associated and/ or Mcat-associated AECOPD.
- Time to first NTHi-associated and/or Mcat-associated AECOPD of any severity.
- Time to first NTHi-associated and/or Mcat-associated AECOPD, by severity.
- Duration of moderate and severe NTHi-associated and Mcat-associated AECOPD.
- Duration of NTHi-associated and/or Mcat-associated AECOPDs of any severity.
- Duration of NTHi-associated and/or Mcat-associated AECOPD, by severity.

Immunogenicity and CMI:

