Note: If the model does not converge, the Poisson distribution will be used instead of the Negative Binomial.

The number of AECOPD occurring from enrolment up to 1 month post-Dose 2 will be used as ‘baseline’ value. No difference between vaccine and placebo is expected in this period.

Descriptive statistics

For each treatment group, the total number of subjects, total number of AECOPD, total exposure time (in days), and incidence exacerbation rate (per year and per each sub period considered) together with the frequency of number of AECOPD will be tabulated.

The following statistics will be reported for exacerbation rate in the two treatment groups: N, mean, SD, median, Q1, Q3, min and max.

Sensitivity analysis

Primary analysis will be presented in three study populations: mTVC, TVC, FAS and PPS. In addition, a sensitivity analysis will be carried out using permutation test.

Permutation test procedure

The null distribution of Z to test H_0 (i.e., $\beta=0$ or $VE=0$) will be obtained by re-randomizing treatment assignment according to the original minimization algorithm (Section 11.3) while keeping outcomes and covariates as observed. The procedure to follow is described below:

1. Fit the regression model to obtain the test statistic Z to test H_0 (i.e., $\beta=0$ or $VE=0$)
2. Estimate the null distribution for the test statistic Z with N (=10000) replicates of the two following steps:

CONFIDENTIAL

207489 (NTHI MCAT-002)

Statistical Analysis Plan Amendment 2 FDA Final Draft

- a. Re-randomize treatment assignment using minimization.
- b. Re-fit the regression model to re-derive the test Z
- 3. Derive the empirical p-value for the test statistic Z from the null distribution based on the permutation distribution

$$p(\text{permutation test}) = (M)/(N)$$

Where M denotes the number of replicates for which the test statistic Z obtained in the permutation procedure is equal to or greater than (in absolute value) the observed value of Z obtained in 1, and N denotes the number of replicates (i.e., 10000).

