Similarly, for the time-to-event and duration of AECOPD data will be also presented for the entire study period starting from Day 1 up to study termination.

In addition, descriptive statistics for the yearly rates and VE will be presented by patient severity (GOLD grade: 2, 3, or 4), by Country (USA, Canada, France, Spain, Belgium, UK, Germany and Italy), by history of exacerbations (< 2 or \geq 2), by usage of inhaled corticosteroid at visit 1 (independently on the start date of usage), by eosinophil level at baseline (<2% or \geq 2%), by NHTi and Mcat presence in sputum at baseline (NTHi alone, Mcat alone, NTHi or Mcat) and by age group (40 - 59 yrs or 60 - 80 yrs).

In addition to the rates of moderate and severe and any severity AECOPD at 3, 6, 9 and 12 months starting 1 month post dose 2, the Kendall-Tau (Kendal Rank correlation Coefficient) test for trend of rates over time will be calculated. A statistically significant correlation between Incidence rates and time period will be concluded if p-value is less than 0.05.

A SAS code similar to the following will be used for this purpose:

```
PROC CORR data=<dataset> kendall;  
class treatment;  
  var rate month;  
by treatmens;  
RUN;
```

CONFIDENTIAL

207489 (NTHI MCAT-002)

Statistical Analysis Plan Amendment 2 FDA Final Draft

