6.3.2. Additional considerations

6.3.2.1. Clinical endpoint

Number of AECOPD

The number of AECOPD occurring during the 1 year follow-up period starting 1 month post-Dose 2 will be used to describe vaccine efficacy (VE). Exacerbation rate reported during this period will be calculated for each subject.

Only for the purpose of reporting summary statistics, the number of exacerbations during the 1-year follow-up will be imputed for subjects withdrawing from the study to provide an estimate of the number of exacerbations over the follow-up period. This calculation will only be performed for the descriptive statistics for the rate of exacerbations during 1 year follow up period since the modelling of exacerbations takes into account the number of exacerbations and the time of follow-up for each subject [see Section 11].

Control of type I error

Inferential analyses for efficacy are planned to be performed at alpha level of 0.13 (two sided). No alpha adjustment for multiple testing in the secondary endpoints will be performed, nevertheless efficacy analysis, both primary and secondary endpoints will be also complemented with the 95% CI.

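### The Kendall tau test for trend in AECOPD rates has four points per arm as written, and no version of its 0.05 rule then gives a 5% two-sided test

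*SAP*

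**What the plan says.** Under the stratification and additional analyses of SAP section 6.3.1.1.2, rates of moderate and severe AECOPD and of AECOPD of any severity are taken "at 3, 6, 9 and 12 months starting 1 month post dose 2", and "the Kendall-Tau (Kendal Rank correlation Coefficient) test for trend of rates over time will be calculated". The decision rule is explicit: "A statistically significant correlation between Incidence rates and time period will be concluded if p-value is less than 0.05".

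The sample code is "PROC CORR data=<dataset> kendall" with "var rate month", run by treatment arm. It requests no exact p-value. The text states neither sidedness nor what one row of the dataset is.

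Two other places bear on the data unit. Section 6.3.1.1.1 tabulates, for each treatment group, the "incidence exacerbation rate (per year and per each sub period considered"), which points to one rate per arm and period. Section 6.3.2.1 says, of the 1-year follow-up, "Exacerbation rate reported during this period will be calculated for each subject".

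On the windows, section 4.2 defines the secondary rates "during 3, 6, 9 and 12 months observation starting 1 month post-Dose 2", which reads as cumulative windows with a common start. The Amendment 2 entry in the document history describes this same test as working by 3-month period, and section 6.3.1.1.2 separately plans yearly rates and VE with 95% CIs by 3-month follow-up period. Both suggest disjoint quarters.

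**The concern.** This is a pre-specified rule for declaring statistical significance, not a descriptive summary. With four points a rank correlation has very few possible p-values, and none need correspond to a 5% error rate. It also takes no account of how many events lie behind each rate, and cumulative windows share events, so successive rates are dependent even when the underlying rate is flat. The study report could therefore state that AECOPD rates rose or fell over the year, in one arm or both, from a test that either cannot reject or rejects more often than stated.

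**Working it through.** **Inputs.** Four time points, Kendall tau, by arm, threshold 0.05 (section 6.3.1.1.2); two-sided, as no direction is given. One rate per arm and period (section 6.3.1.1.1). About 300 subjects per arm (section 2). The SAP gives no event rate or dispersion for this analysis. The simulations assume 0.8 to 2.0 events per year, negative binomial dispersion 0 to 1.0, a constant rate and equal follow-up in each quarter.

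**Exact test, n = 4.** There are 4! = 24 orderings of the rates. Only two, fully increasing and fully decreasing, give |tau| = 1. The smallest two-sided p is 2/24 = 0.0833, so rejection at 0.05 is impossible whatever the data.

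**Normal approximation, n = 4.** Let S be the number of concordant pairs minus the number of discordant pairs.
- Var(S) = n(n-1)(2n+5)/18 = 4 × 3 × 13/18 = 8.667.
- Perfect order, |S| = 6: z = 6/√8.667 = 2.038, p = 0.0415.
- Next outcome, |S| = 4: z = 4/√8.667 = 1.359, p = 0.174.
- Perfect order with continuity correction: z = 5/√8.667 = 1.698, p = 0.089.

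So the uncorrected version rejects only on a perfectly monotone order, and the corrected version never rejects. The true size of the uncorrected version is the probability of that order when the rate is constant.

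**Disjoint quarters.** The four rates are exchangeable, so the probability is 2/24 = 8.3%. Event counts can tie. One tied pair leaves |S| at most 5 with Var(S) = (156 - 18)/18 = 7.667, so z = 1.81 and p = 0.071, which is no rejection. Simulated size allowing for ties was 6.6% to 7.3%.

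**Cumulative windows.** Let X1 to X4 be the quarterly rates. The successive changes in the cumulative rate are (X2 - X1)/2, then X3 minus the mean of X1 and X2, divided by 3, then X4 minus the mean of X1 to X3, divided by 4. In the normal limit these are independent and symmetric about zero. The probability that all three have the same sign is 2 × (1/2)³ = 25%. Simulated with counts, 23.2% to 23.9%.

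**One row per subject and period** (300 × 4 rows per arm, rates 1.0 and 1.5 per year, dispersion 0.5 and 1.0). The 0.083 floor no longer applies. Disjoint quarters rejected in 2.5% to 3.5% of null trials, cumulative windows in more than 99%.

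| Reading | True size at nominal 0.05 |
|---|---|
| Arm level, exact two-sided | 0% |
| Arm level, asymptotic, disjoint | 8.3% (6.6-7.3% with ties) |
| Arm level, asymptotic, cumulative | 25% (23.2-23.9% with counts) |
| Subject level, disjoint | 2.5-3.5% |
| Subject level, cumulative | over 99% |

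**The case against.** The strongest reply is that several of these readings are inferred. The dataset is left unspecified, the code is offered only as similar to what will be used, and neither the type nor the sidedness of the p-value is stated. A one-sided exact test could reach 1/24 = 0.042, and subject-level rows on disjoint quarters would give a usable, mildly conservative test. All of that is fair, and it limits how far the point can be pressed. It does not rescue the rule: the SAP specifies no one-sided test, its description of rates by group and sub-period points to arm-level data, and no arm-level two-sided version gives 5%.

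Three stronger readings are tempting and are not supported.
- A reader might infer that every version rejects far above 5%. Only the cumulative version does. The asymptotic test on disjoint quarters is mildly inflated.
- A reader might take the cumulative windows as settled. Section 4.2 and the wording of the test suggest them, but the document history and the planned 3-month tabulation suggest disjoint quarters. The 23-24% figure is conditional on the first reading.
- A reader might fault the test for not showing whether efficacy wanes. A within-arm trend indeed cannot separate waning from season or time on study, but the SAP claims only a trend in rates and already plans VE by 3-month period. A test of waning would be an added objective.

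**Conclusion.** The rule is wrong as written. With one rate per arm and period, the stated 0.05 criterion has true two-sided size 0% (exact), about 7-8% (asymptotic, disjoint quarters) or about 23-25% (asymptotic, cumulative windows). The exact floor and the 8.3% follow from counting orderings. The count-based ranges rest on the assumed 300 subjects per arm and 0.8 to 2.0 events a year, and vary little across those assumptions. The choice between cumulative and disjoint windows, the data unit and the type of p-value all need to be stated, because the size depends heavily on them. The consequence is limited: this is an additional analysis among the secondary ones, without multiplicity control, and it does not bear on the primary criterion based on the 87% CI.

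**What to change.** State in section 6.3.1.1.2 that the trend is assessed over four disjoint 3-month periods from 1 month post-Dose 2. Replace the Kendall test with a log-linear count model on subject-by-quarter counts, fitted by GEE clustered on subject, with log days observed in the quarter as offset and the minimisation factors (country, GOLD grade, exacerbation history, age group) as covariates. Test the linear quarter term within each arm. That answers the stated question, weights each quarter by its information and allows for repeated counts on a subject. A treatment-by-quarter term may be added as an optional test of change in VE, alongside the VE by 3-month period already planned.

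At minimum, delete the 0.05 conclusion and present the quarterly rates by arm with 95% CIs, descriptively.

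The cost is a paragraph of SAP text and a short program. No new data are needed, since rates by 3-month period are already to be tabulated.

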6.3.1.2. Efficacy – Bacteriological Endpoint (PCR)

An AECOPD will be considered ‘associated’ to NTHi and/or Mcat if the sputum sample, collected during AECOPD visit, will reveal the presence of those bacteria.

We can assume that more than 99% of *H. influenzae* isolates in sputum (derived from lung) are non-typeable (NTHi) [Wilkinson, 2017] and thus the presence of Hi bacteria in sputum during exacerbation will be used to determine AECOPD associated to NTHi.

In case of no sputum sample at such visit, or no bacteriological presence (i.e., Hi or Mcat) the event will not be counted.

Bacteriological vaccine efficacy (VE_{bact}) is defined as reduction in number of NTHi and/or Mcat associated AECOPD in vaccinated subjects compared to placebo subjects:

$$VE_{bact} = 1 - R_{vacc} / R_{con}$$

where

- R_{vacc} = average yearly incidence rate of AECOPD events associated to NTHi and/or Mcat per subject in the group 10-10-3-AS.
- R_{con} = average yearly incidence rate of AECOPD events associated to NTHi and/or Mcat per subject in the placebo group.

VE_{bact} in prevention of NTHi and/or Mcat associated AECOPD will be evaluated via PCR method in all subjects. The statistical analysis will be performed in a modified TVC (mTVC) population as first line and repeated in the PPS cohort if more than 5% of subjects are excluded.

The mTVC is defined as all subjects in the TVC (i.e. ES) who provide sputum sample results.

The following incidence rate together and VE_{bact} over a period starting 1 month post-Dose 2 and lasting for 1 year and its 95% CIs will be computed:

- NTHi and/or Mcat-associated moderate and severe AECOPD.
- NTHi and/or Mcat-associated all-severity AECOPD.
- NTHi and/or Mcat-associated AECOPD, by severity.
- The time until first moderate and severe NTHi and/or Mcat- associated AECOPD.
- The time until first NTHi and/or Mcat- associated AECOPD (any severity).
- The time until first NTHi and/or Mcat- associated AECOPD by severity.

In addition yearly rates of AECOPD associated to NTHi and/or Mcat, and VE_{bact} , together with 95% CIs will be evaluated for the following time periods:

- By 6 Months follow-up period (from 1 month post-Dose 2)
- By 3 Months follow-up period (from 1 month post-Dose 2)

CONFIDENTIAL207489 (NTHI MCAT-002)
Statistical Analysis Plan Amendment 2 FDA Final DraftInferential statistic

Number and proportion of sputum samples (obtained at each scheduled visit and at each AECOPD visit) positive for bacterial pathogens (Hi and/or Mcat) will be computed together with exact 95% CIs by group and overall. The exact CIs will be estimated assuming independence of bacterial results across sputum samples.

The bacteriological vaccine efficacy outcome will be evaluated using same model as for clinical efficacy with the following SAS code:

```
PROC GENMOD data=<dataset>;
  CLASS trt age gold hexac country;
  MODEL nb_bact_exac = trt age gold hexac country
    / dist=NegBin LINK=log OFFSET=logfu;
RUN;
```

Where

nb_bact_exac are AECOPD associated to NTHi and/or Mcat by PCR method

As for the primary endpoint the number of bacterial associated AECOPD occurring from enrolment up to 1 month post-Dose 2 will be used as 'baseline' value. No difference between vaccine and placebo is expected in this period.

Descriptive statistics

For each treatment group, the total number of subjects, total number of AECOPD associated to NTHi and/or Mcat, total exposure time (in days), incidence of bacteriological associated exacerbation rate (per year and per each sub period considered) and the frequency of number of AECOPD will be tabulated.

The following statistics will be reported for AECOPD associated to NTHi and /or Mcat: N, mean, SD, median, Q1, Q3, min and max.

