2. STUDY DESIGN

Figure 1 Study design overview

S = Screening Visit; V = Visit; PC = Phone contact; D = Day; FU = Follow-up; BS (1) = blood sample for humoral immunogenicity; BS (2) = blood sample for cell-mediated immunogenicity (CMI), this blood sample will only be collected from a sub-cohort of subjects; BS (3) blood sample for biomarkers; SP = sputum sample

The allowed maximum interval between Screening Visit and Visit 1 is 29 days. If a delay occurs for an eligible subject so that the interval exceeds 29 days, some study procedures performed during the Screening Visit needs to be repeated within 7 days (see Table 6 of the protocol for more details).

* An AECOPD visit should be scheduled as soon as possible after the onset of AECOPD symptoms (max 96 hours after and, if applicable, preferably before starting treatment with antibiotics) During this visit blood and sputum samples will be collected. In addition, follow-up phone call(s) and/or visit(s) will take place to determine the end of the AECOPD. These contacts will take place at least every 2 weeks until the AECOPD is resolved.

Investigational vaccine and placebo will be administered in addition to standard of care.

- **Experimental design:** Phase IIB, randomised, observer-blind, placebo-controlled, multi-centric study with two parallel groups.
- **Duration of the study:** for each subject enrolled, the study will last approximately 15 months from Visit 1 up to study completion (Visit 8).
 - Epoch 001: Screening Visit (Day -28 to Day -1).
 - Epoch 002 : Primary starting at Visit 1 (Day 1) and ending at Visit 8 (Day 451).
- **Primary completion Date (PCD):** Last Subject Last Visit (LSLV) from Visit 8 (Day 451) or last visit/contact of Epoch 002.
- **Study groups:**
 - **10-10-3-AS:** Approximately 300 subjects receiving two doses of the AS01_E-adjuvanted GSK Biologicals' NTHi-Mcat investigational vaccine containing 10 µg of PD, 10 µg of PE-PilA, and 3.3 µg of UspA2.
 - **CONTROL:** Approximately 300 subjects receiving two doses of placebo (PBS).

CONFIDENTIAL

207489 (NTHI MCAT-002)

Statistical Analysis Plan Amendment 2 FDA Final Draft

The following group names will be used for the statistical analysis

Table 1 Study groups and epochs foreseen in the study

Group order in tables	Number of subjects	Group label in tables	Group definition for footnote
1	~300	10-10-3-AS	2 doses of AS01E-adjuvanted NTHI/Mcat vaccine containing 10 mcg of PD, PE-PiA and 3 mcg of UspA2

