2	~300	PLACEBO	2 doses of phosphate buffered solution

- **Sampling schedule:**

- **Blood samples for assessment of humoral immunogenicity** will be collected from all subjects at Visit 1 (Day 1), Visit 2 (Day 31), Visit 3 (Day 61), Visit 4 (Day 91), Visit 6 (Day 271), Visit 8 (Day 451) and at each AECOPD visit from first vaccination to study conclusion.
- **Blood samples for assessment of cell-mediated immunogenicity (CMI)** will be collected from all subjects in the CMI sub-cohort (approximately 60 subjects in each group) at Visit 1 (Day 1), Visit 4 (Day 91), Visit 6 (Day 271) and at Visit 8 (Day 451).
- **Blood samples for biomarkers** will be collected from all subjects at Visit 1 (Day 1), Visit 8 (Day 451) and at each AECOPD visit from first vaccination to study conclusion.
- **Blood sample for haematology profile** will only be collected at Visit 1.
- **Sputum samples for PCR (all subjects) and culture** (50% of subjects) will be collected from all subjects at Visit 1 (Day 1), Visit 4 (Day 91), Visit 5 (Day 181), Visit 6 (Day 271), Visit 7 (Day 361), Visit 8 (Day 451) and at each AECOPD visit from first vaccination to study conclusion.

Other assessments:

- **COPD symptoms:** All subjects will be asked to record COPD symptoms in their electronic Diary Card:
 - Daily in the morning throughout the study (including during AECOPD): **morning symptoms questionnaire**.
 - Daily in the evening throughout the study (including during AECOPD): **EXACT-PRO questionnaire**.
- **HRQOL assessments:**
 - All subjects will be asked to complete the COPD assessment test (CAT) at the Screening Visit (pre-Day 1), Visit 6 (Day 271), Visit 8 (Day 451) and at each AECOPD visit from first vaccination to study conclusion.
 - All subjects will be asked to complete St. George's Respiratory Questionnaire for COPD patients (SGRQ-C) at the Screening Visit (pre-Day 1), Visit 6 (Day 271), at Visit 8 (Day 451) and at each AECOPD visit from first vaccination to study conclusion.

CONFIDENTIAL

207489 (NTHI MCAT-002)

Statistical Analysis Plan Amendment 2 FDA Final Draft

Pre- and post-bronchodilator spirometry assessments will be done for all subjects at the Screening Visit (pre-Day 1), Visit 6 (Day 271) and at Visit 8 (Day 451).

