4.3. Tertiary endpoints**Sputum sample PCR:**

- Occurrence (presence and absence), bacterial load measured by PCR of NTHi and/or Mcat in sputum before first vaccination and at Day 91, Day 181, Day 271, Day 361 and Day 451 and at each AECOPD visit.
- Number of acquisitions and apparitions of NTHi and Mcat bacteria in sputum collected from Day 1 and from Day 91 and analysed by PCR.

Sputum sample culture:

- Occurrence (presence and absence), and semi-quantitative bacterial load measured in a subset of sputum sample by culture of NTHi and/or Mcat in sputum before first vaccination and at Day 91, Day 181, Day 271, Day 361 and Day 451 and at each AECOPD visit.

CONFIDENTIAL

207489 (NTHI MCAT-002)

Statistical Analysis Plan Amendment 2 FDA Final Draft

- Number of acquisitions and with apparitions of NTHi and Mcat bacteria in sputum collected from Day 1 and from Day 91 and analysed by culture.
- Rate of NTHi-associated and Mcat-associated, moderate and severe AECOPD.
- Rate of NTHi-associated and Mcat-associated any severity AECOPD.
- Rate of NTHi-associated and Mcat-associated AECOPD, by severity.
- Time to first moderate or severe NTHi-associated and/or Mcat-associated AECOPD.
- Time to first any NTHi-associated and rate Mcat-associated AECOPD.
- Time to first NTHi-associated and rate Mcat-associated AECOPD, by severity.
- Duration of each moderate and severe NTHi-associated and Mcat-associated AECOPD.
- Duration of NTHi-associated and/or Mcat-associated AECOPDs of any severity.
- Duration of NTHi-associated and/or Mcat-associated AECOPD, by severity.

QOL:

- Assessment of EXACT-PRO score, daily in the evening throughout the study, in all subjects.
- Assessment of CAT scores at Screening, Day 271 and Day 451, and from first vaccination to study conclusion for each AECOPD visit, in all subjects.
- Assessment of SGRQ-C score at Screening, Day 271 and Day 451, and from first vaccination to study conclusion for each AECOPD visit, in all subjects.
- Assessment of use of medication to treat (AE)COPD and healthcare utilization in all subjects throughout the study period.

Lung function:

- Assessment of FEV1% of predicted normal value at Screening, Day 271 and Day 451, in all subjects.

Biomarkers:

- Concentration of selected biomarkers (fibrinogen, hsCRP and IP-10), at Day 1 and Day 451, and for each AECOPD visit from first vaccination to study conclusion.

T helper profile:

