8. CONDUCT OF ANALYSES

The analysis planned in this study will be performed in four steps giving higher priority to the most relevant objectives (i.e., primary, secondary)

Specifically, the analyses will be released in this order:

- Priority 1 analyses will be released at first and reported in a full clinical study report (CSR), this analysis is performed in to two steps:
 - Step 1: Analysis of primary efficacy endpoint and secondary safety endpoint.
 - Step 2: Analysis of immunogenicity, CMI and bacteriological PCR secondary endpoints plus the following tertiary objectives:
 - To evaluate the effect of the investigational vaccine on the presence and load of NTHi and/or Mcat at stable visits and AECOPD by PCR.
 - To explore the impact of the investigational vaccine on health-related quality of life (HRQOL).
 - To explore the T helper profile of the PD-, PE-, PilA-, UspA2-specific CD4+/ CD8+ T cell responses
- Priority 2 analysis will be released in a third step and reported in to an Annex report. They include, the following tertiary objectives:
 - *To evaluate the effect of the investigational vaccine on the presence, acquisition/apparition and load of NTHi and/or Mcat at stable visits and AECOPD by culture.*
 - *To evaluate the effect of the investigational vaccine on the presence, acquisition/apparition and load of NTHi and/or Mcat at stable visits and AECOPD by culture. To explore the efficacy of the investigational vaccine as compared to placebo with respect to the rate of all AECOPDs and by severity (i.e. mild, moderate or severe) associated with NTHi and/or Mcat detected in a subset of sputum samples by culture.*
 - *To explore the impact of the investigational vaccine on use of medication for COPD and Healthcare Resource Utilization.*
 - *To explore the impact of the investigational vaccine on lung function.*
 - *To describe selected biomarkers in stable COPD and during AECOPD*

and other stratified analyses to evaluate VE in subsets:

- Vaccine efficacy (clinical and bacteriological) by eosinophil level in blood at baseline
- Vaccine efficacy (clinical and bacteriological) by NTHi presence in sputum (detected by PCR) at baseline
- Vaccine efficacy (clinical and bacteriological) by Mcat presence in sputum (detected by PCR) at baseline

CONFIDENTIAL

207489 (NTHI MCAT-002)

Statistical Analysis Plan Amendment 2 FDA Final Draft

- Vaccine efficacy (clinical and bacteriological) by NTHi or Mcat presence in sputum (detected by PCR) at baseline

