11.3. Randomization method and minimization algorithm

Subjects are randomised using a centralised randomisation system on internet (SBIR) at first dose. The system incorporates a minimization algorithm based on White SJ and Freedam LS method [[White SJ](#), Freedman LS, 1978] and it is described below:

Notation:

- k input values to be used for minimization, each with a weight w_k ($k=1, \dots, K$) and l_k variants.
- i treatment groups applicable to stratum the subject has been identified with randomization ratio a_1, \dots, a_i
- D: percentage of determinism
- W: weight assigned to each minimization factor

In this study k=4: Country, GOLD grade, History of exacerbation and Age group defined as :

COUNTRY [8 variants]: BE CA FR DE IT ES UK US

GOLD [3 variants]: 2 3 4

AGECAT [2 variants]: 40-60 61-80

HIST_ES [2 variants]: < 2 >=2

i=2: VACCINE and PLACEBO with randomization ratio 1:1 ($a_i=1$)

D=90%

W=1 for each variable

CONFIDENTIAL207489 (NTHI MCAT-002)
Statistical Analysis Plan Amendment 2 FDA Final Draft

Algorithm:

For a new subject in criteria levels $s_1 \dots s_k$ **Step 1: Minimization computation**

Step 1.1: Initialize Problem flag to 0

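### The VE_bact model omits Day 1 Hi/Mcat sputum status, a likely predictor already collected; adding it is a cheap, modest gain for a secondary endpoint

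*SAP*

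**What the plan says.** In the current SAP (Amendment 2), section 6.3.1.2 evaluates VE_bact with the same model as the clinical endpoint. The model line is "MODEL nb_bact_exac = trt age gold hexac country" and the options are "dist=NegBin LINK=log OFFSET=logfu", so the covariates are age group, GOLD grade, exacerbation history and country.

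Four other places bear on this:

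- **Collection.** Section 2 plans PCR sputum that "will be collected from all subjects at Visit 1 (Day 1), Visit 4 (Day 91), Visit 5 (Day 181" and at later visits. Section 4.3 lists as a tertiary endpoint the "bacterial load measured by PCR of NTHi and/or Mcat in sputum before first vaccination".
- **Allocation.** Section 11.3 names the minimisation factors: "In this study k=4: Country, GOLD grade, History of exacerbation and Age group". Carriage is not one of them.
- **Use of baseline carriage.** Section 6.3.1.1.2 presents rates and VE by NTHi and Mcat presence at baseline. Section 8 lists, among the Priority 2 analyses, "Vaccine efficacy (clinical and bacteriological) by NTHi presence in sputum (detected by PCR) at baseline", with matching lines for Mcat and for either organism.
- **What the plan calls baseline.** Section 6.3.1.2 gives that label to the number of bacteria-associated AECOPD between enrolment and one month after Dose 2. That count is not in the model line either.

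VE_bact is a secondary endpoint. Section 7 gives it 95% confidence intervals without multiplicity adjustment, and no success criterion is attached to it.

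**The concern.** An AECOPD enters VE_bact when the sputum taken at the AECOPD visit shows Hi or Mcat, and section 6.6.1.2 defines qPCR positivity as a result at or above the limit of detection. New acquisition is not required. A subject who already carries the organism may therefore contribute a counted event even when something else caused the exacerbation, so Day 1 carriage is a plausible predictor of this particular count.

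If it is a predictor, leaving it out moves explainable variation into the dispersion parameter and widens the interval for VE_bact. A chance difference in carriage between the arms also stays in the point estimate. The planned splits by baseline carriage would show such a difference but do not adjust the overall VE_bact. Elsewhere the plan does adjust for a pre-treatment value: pre-dose concentration in the antibody ANCOVA (section 6.4.1) and the screening score in the EXACT-PRO ANCOVA (section 6.6.2).

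**Working it through.** The SAP states no power, event count or precision for VE_bact, so there is no figure of its own to reproduce. The check compares the standard error of the log rate ratio with and without a binary carriage covariate.

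**Inputs from the SAP.** About 300 subjects per group (section 2); "i=2: VACCINE and PLACEBO with randomization ratio 1:1" (section 11.3); negative binomial model with log link; one year of follow-up from one month after Dose 2; two-sided 95% intervals.

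**Assumed, because the SAP does not give them.** Carriage prevalence p = 0.2 to 0.4; carrier to non-carrier rate ratio R = 1.5 to 3; overall rate r = 0.3 to 0.8 Hi/Mcat-associated AECOPD per year; residual dispersion k = 0.5 to 1.0. Follow-up is complete, every subject has a Day 1 result, and the other covariates are left out of both models.

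**Formulas (no vaccine effect).**

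- Information per subject: mu/(1 + k·mu).
- Non-carrier rate: m0 = r/(1 − p + pR); carrier rate: R·m0.
- Adjusted SE = sqrt(2/I), where I is 300 times the prevalence-weighted mean of the per-subject information.
- Unadjusted: the omitted factor inflates the dispersion to ku = (1 + k)(1 + v) − 1, with v = [(1 − p)·m0² + p·(R·m0)²]/r² − 1. Then SE = sqrt(2/(300·r/(1 + ku·r))).

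**One case in full: r = 0.5, p = 0.2, R = 3, k = 1.**

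- m0 = 0.5/1.4 = 0.357; carrier rate 1.071.
- v = (0.8 × 0.1276 + 0.2 × 1.1480)/0.25 − 1 = 0.327; ku = 2 × 1.327 − 1 = 1.653.
- Unadjusted: 0.5/(1 + 0.827) = 0.2737; × 300 = 82.1; SE = sqrt(2/82.1) = 0.156.
- Adjusted: 0.8 × 0.2632 + 0.2 × 0.5172 = 0.3140; × 300 = 94.2; SE = sqrt(2/94.2) = 0.146.
- Ratio 1.071; 1.071² − 1 = about 15% more patients needed without the covariate.

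**Over the whole grid.**

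| Carrier rate ratio | SE unadjusted / adjusted | Extra patients needed |
|---|---|---|
| 1.5 | 1.005 to 1.013 | 0.9% to 2.7% |
| 2 | 1.015 to 1.038 | 3.1% to 7.8% |
| 3 | 1.039 to 1.101 | 7.9% to 21.1% |

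**Simulation** (400 trials per setting, both models fitted to the same data; r = 0.5, p = 0.3, k = 0.8).

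| Setting | Unadjusted | Adjusted |
|---|---|---|
| VE 0, ratio 2: mean log RR; rejection rate | −0.015; 0.060 | −0.013; 0.058 |
| VE 0, ratio 3: mean log RR; rejection rate | 0.001; 0.052 | 0.000; 0.055 |
| VE 30%, ratio 2: power | 66.8% | 68.5% |
| VE 30%, ratio 3: power | 62.5% | 66.0% |

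The Monte Carlo error of a rejection rate near 0.05 is sqrt(0.05 × 0.95/400) = 0.011, so none of the null rates differs from 0.05 by more than chance. The power gains are 1.7 and 3.5 points.

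**Chance imbalance at 30% carriage.** The SD of the difference in prevalence is sqrt(2 × 0.3 × 0.7/300) = 3.7 points; 1.96 SD is 7.3 points, that is 33.7% against 26.3%. With R = 3 the rate ratio is multiplied by (1 + 2 × 0.337)/(1 + 2 × 0.263) = 1.096, or by its inverse 0.912. With a true VE of 0, the apparent VE would be about −10% or +9%. At one SD (31.9% against 28.1%) the factor is 1.637/1.563 = 1.05.

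**The case against.** A reader might infer that VE_bact is biased, that the plan forgot the endpoint's own baseline, or that nothing balances carriage between the arms. The documents support none of these. The outcome is a count of exacerbations, and Day 1 carriage is only a candidate predictor of it; exacerbation history is already in the model. Random allocation balances carriage in expectation. With a log link, omitting an independent covariate leaves the rate ratio unchanged on average, and the simulation shows neither bias nor excess rejections. The 9% to 10% shift needs both a 1.96-SD imbalance and a threefold carrier effect, and the unadjusted interval already allows for imbalance of that kind.

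The other side can add that the model covers all four minimisation factors, that bacteriological VE by baseline carriage is planned, and that Day 1 positivity is tabulated by group, so an imbalance would be visible. Larger gains can be produced by assuming carriers have four to six times the event rate. Nothing in the SAP supports that: counting starts about three months after the Day 1 sample, and the plan's own acquisition and apparition analyses treat carriage as something that changes.

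All of this stands, and it removes any claim of invalidity. It does not answer the efficiency point, because neither the splits nor the tabulation adjusts the overall VE_bact.

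Two cautions also stand and limit the fix. In the Cox model for time to first event, adding a prognostic covariate generally changes the hazard ratio being estimated (non-collapsibility). In the by-severity, 3-month and culture analyses, a further factor beside eight countries may hinder convergence, and section 6.3.1.1.1 then falls back to a Poisson model.

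**Conclusion.** The point holds as a low-cost improvement to a secondary endpoint. The planned VE_bact analysis is valid as written. If Day 1 carriage predicts Hi/Mcat-associated AECOPD, the plan gives up a small to modest amount of precision and leaves chance imbalance in carriage uncorrected. The gain is negligible if carriage is weakly prognostic, and it would be smaller than computed if GOLD grade, exacerbation history or country already carries part of the same information, or if many Day 1 samples are missing. No pre-specified decision depends on it. It is still worth settling before unblinding, because carriage imbalance is an obvious challenge to any VE_bact result and adjustment chosen afterwards would be post hoc.

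**What to change.** In section 6.3.1.2, add Day 1 Hi/Mcat PCR status as a class covariate with three levels: negative; positive (Hi or Mcat at or above the limit of detection in section 6.6.1.2); no valid sample. Apply it to the 12-month negative binomial models for moderate/severe and for any-severity Hi/Mcat-associated AECOPD, and keep the current model as a pre-specified sensitivity analysis.

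For the time-to-first Cox model and the by-severity and 3-month analyses, use the covariate only as a sensitivity analysis where event counts allow. Do the same in the culture subset.

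Do not use the bacteria-associated AECOPD count from Day 1 to Day 90 as a covariate: it accrues after randomisation and the first dose.

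The cost is a line or two of SAP text, two degrees of freedom and a missing category. No new data are needed.
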